11.1.7 Response Review

All responses will be reviewed by the radiology investigator of the study at the study's completion to allow simultaneous review of the patients' files and radiological images. Raw data from baseline and follow up MRI will be obtained from the participating institutions for volumetric, perfusion and diffusion-based response assessments. Sites should send anonymized pre- and post-treatment scans via FTP or as a hard copy CD to the study PI, [name] at the University of Maryland, as listed on the title page. The scans and data will be stored in HIPAA compliant secure servers within the Department of Radiology. Each patient will be identified only with the patient number assigned by the study.

12. STUDY OVERSIGHT AND DATA REPORTING / REGULATORY REQUIREMENTS

Adverse event lists, guidelines, and instructions for AE reporting can be found in Section 7.0 (Adverse Events: List and Reporting Requirements).

12.1 Study Oversight

This protocol is monitored at several levels, as described in this section. The Protocol Principal Investigator is responsible for monitoring the conduct and progress of the clinical trial, including the ongoing review of accrual, patient-specific clinical and laboratory data, and routine and serious adverse events; reporting of expedited adverse events; and accumulation of reported adverse events from other trials testing the same drug(s). The Protocol Principal Investigator and statistician have access to the data at all times through the CTMS web-based reporting portal.

For the Phase 1 portion of this study, all decisions regarding dose escalation/expansion/de-escalation require sign-off by the Protocol Principal Investigator through the CTMS/IWRS. In addition, for the Phase 1 portion, the Protocol Principal Investigator will have at least monthly, or more frequently, conference calls with the Study Investigators and the CTEP Medical Officer(s) to review accrual, progress, and adverse events and unanticipated problems.

All Study Investigators at participating sites who register/enroll patients on a given protocol are responsible for timely submission of data via Medidata Rave and timely reporting of adverse events for that particular study. This includes timely review of data collected on the electronic CRFs submitted via Medidata Rave.

All studies are also reviewed in accordance with the enrolling institution's data safety monitoring plan.

12.2 Data Reporting

Data collection for this study will be done exclusively through Medidata Rave. Access to the trial in Rave is granted through the iMedidata application to all persons with the appropriate roles assigned in the Regulatory Support System (RSS). To access Rave via iMedidata, the site user must have an active CTEP IAM account (check at <<https://ctepcore.nci.nih.gov/iam>>) and the appropriate Rave role (Rave CRA, Read-Only, CRA (Lab Admin, SLA or Site Investigator) on either the LPO or participating organization roster at the enrolling site. To the hold Rave CRA role or CRA Lab Admin role, the user must hold a minimum of an AP registration type. To hold the Rave Site Investigator role, the individual must be registered as an NPIVR or IVR. Associates can hold read-only roles in Rave. If the study has a DTL, individuals requiring write access to Rave must also be assigned the appropriate Rave tasks on the DTL..

Upon initial site registration approval for the study in RSS, all persons with Rave roles

assigned on the appropriate roster will be sent a study invitation e-mail from iMedidata. To accept the invitation, site users must log into the Select Login (<https://login.imedidata.com/selectlogin>) using their CTEP-IAM user name and password and click on the “accept” link in the upper right-corner of the iMedidata page. Please note, site users will not be able to access the study in Rave until all required Medidata and study specific trainings are completed. Trainings will be in the form of electronic learnings (eLearnings), and can be accessed by clicking on the link in the upper right pane of the iMedidata screen.

Users that have not previously activated their iMedidata/Rave account at the time of initial site registration approval for the study in RSS will also receive a separate invitation from iMedidata to activate their account. Account activation instructions are located on the CTSU website, Rave tab under the Rave resource materials (Medidata Account Activation and Study Invitation Acceptance). Additional information on iMedidata/Rave is available on the CTSU members’ website under the Rave tab or by contacting the CTSU Help Desk at [name] or by e-mail at [contact].

12.2.1 Method

This study will be monitored by the Clinical Trials Monitoring Service (CTMS). Data will be submitted to CTMS at least once every two weeks via Medidata Rave (or other modality if approved by CTEP). Information on CTMS reporting is available at <http://www.theradex.com/clinicalTechnologies/?National-Cancer-Institute-NCI-11>. On-site audits will be conducted three times annually (one annual site visit and two data audits). For CTMS monitored studies, after users have activated their accounts, please contact the Theradex Help Desk at [contact] or by email at [contact] for additional support with Rave and completion of CRFs.

12.2.2 Responsibility for Data Submission

For ETCTN trials, it is the responsibility of the PI(s) at the site to ensure that all investigators at the ETCTN Sites understand the procedures for data submission for each ETCTN protocol and that protocol specified data are submitted accurately and in a timely manner to the CTMS via the electronic data capture system, Medidata Rave.

Data are to be submitted via Medidata Rave to CTMS on a real-time basis, but no less than once every 2 weeks. The timeliness of data submissions and timeliness in resolving data queries will be tracked by CTMS. Metrics for timeliness will be followed and assessed on a quarterly basis. For the purpose of Institutional Performance Monitoring, data will be considered delinquent if it is greater than 4 weeks past due.

Data from Medidata Rave and CTEP-AERS is reviewed by the CTMS on an ongoing basis as data is received. Queries will be issued by CTMS directly within Rave. The queries will appear on the Task Summary Tab within Rave for the CRA at the ETCTN to resolve. Monthly web-based reports are posted for review by the Drug Monitors in

the IDB, CTEP. Onsite audits will be conducted by the CTMS to ensure compliance with regulatory requirements, GCP, and NCI policies and procedures with the overarching goal of ensuring the integrity of data generated from NCI-sponsored clinical trials, as described in the ETCTN Program Guidelines, which may be found on the CTEP (http://ctep.cancer.gov/protocolDevelopment/electronic_applications/adverse_events.htm) and CTSU websites.

An End of Study CRF is to be completed by the PI and is to include a summary of study endpoints not otherwise captured in the database, such as (for phase 1 trials) the recommended phase 2 dose (RP2D), and a description of any dose-limiting toxicities (DLTs). CTMS will utilize a core set of eCRFs that are Cancer Data Standards Registry and Repository (caDSR) compliant (<http://cbiit.nci.nih.gov/ncip/biomedical-informatics-resources/interoperability-and-semantics/metadata-and-models>). Customized eCRFs will be included when appropriate to meet unique study requirements. The PI is encouraged to review the eCRFs, working closely with CTMS to ensure prospectively that all required items are appropriately captured in the eCRFs prior to study activation. CTMS will prepare the eCRFs with built-in edit checks to the extent possible to promote data integrity.

CDUS data submissions for ETCTN trials activated after March 1, 2014, will be carried out by the CTMS contractor, Theradex. CDUS submissions are performed by Theradex on a monthly basis. The trial's lead institution is responsible for timely submission to CTMS via Rave, as above.

Further information on data submission procedures can be found in the ETCTN Program Guidelines (http://ctep.cancer.gov/protocolDevelopment/electronic_applications/adverse_events.htm).

12.3 CTEP Multicenter Guidelines

Not Applicable

12.4 Collaborative Agreements Language

The agent(s) supplied by CTEP, DCTD, NCI used in this protocol is/are provided to the NCI under a Collaborative Agreement (CRADA, CTA, CSA) between the Pharmaceutical Company(ies) (hereinafter referred to as "Collaborator(s)") and the NCI Division of Cancer Treatment and Diagnosis. Therefore, the following obligations/guidelines, in addition to the provisions in the "Intellectual Property Option to Collaborator" (http://ctep.cancer.gov/industryCollaborations2/intellectual_property.htm) contained within the terms of award, apply to the use of the Agent(s) in this study:

1. Agent(s) may not be used for any purpose outside the scope of this protocol, nor can Agent(s) be transferred or licensed to any party not participating in the

clinical study. Collaborator(s) data for Agent(s) are confidential and proprietary to Collaborator(s) and shall be maintained as such by the investigators. The protocol documents for studies utilizing Agents contain confidential information and should not be shared or distributed without the permission of the NCI. If a copy of this protocol is requested by a patient or patient's family member participating on the study, the individual should sign a confidentiality agreement. A suitable model agreement can be downloaded from: <http://ctep.cancer.gov>.

2. For a clinical protocol where there is an investigational Agent used in combination with (an)other Agent(s), each the subject of different Collaborative Agreements, the access to and use of data by each Collaborator shall be as follows (data pertaining to such combination use shall hereinafter be referred to as "Multi-Party Data"):
 - a. NCI will provide all Collaborators with prior written notice regarding the existence and nature of any agreements governing their collaboration with NCI, the design of the proposed combination protocol, and the existence of any obligations that would tend to restrict NCI's participation in the proposed combination protocol.
 - b. Each Collaborator shall agree to permit use of the Multi-Party Data from the clinical trial by any other Collaborator solely to the extent necessary to allow said other Collaborator to develop, obtain regulatory approval or commercialize its own Agent.
 - c. Any Collaborator having the right to use the Multi-Party Data from these trials must agree in writing prior to the commencement of the trials that it will use the Multi-Party Data solely for development, regulatory approval, and commercialization of its own Agent.
3. Clinical Trial Data and Results and Raw Data developed under a Collaborative Agreement will be made available to Collaborator(s), the NCI, and the FDA, as appropriate and unless additional disclosure is required by law or court order as described in the IP Option to Collaborator (http://ctep.cancer.gov/industryCollaborations2/intellectual_property.htm). Additionally, all Clinical Data and Results and Raw Data will be collected, used and disclosed consistent with all applicable federal statutes and regulations for the protection of human subjects, including, if applicable, the Standards for Privacy of Individually Identifiable Health Information set forth in 45 C.F.R. Part 164.
4. When a Collaborator wishes to initiate a data request, the request should first be sent to the NCI, who will then notify the appropriate investigators (Group Chair for Cooperative Group studies, or PI for other studies) of Collaborator's wish to contact them.
5. Any data provided to Collaborator(s) for Phase 3 studies must be in accordance

with the guidelines and policies of the responsible Data Monitoring Committee (DMC), if there is a DMC for this clinical trial.

6. Any manuscripts reporting the results of this clinical trial must be provided to CTEP by the Group office for Cooperative Group studies or by the principal investigator for non-Cooperative Group studies for immediate delivery to Collaborator(s) for advisory review and comment prior to submission for publication. Collaborator(s) will have 30 days from the date of receipt for review. Collaborator shall have the right to request that publication be delayed for up to an additional 30 days in order to ensure that Collaborator's confidential and proprietary data, in addition to Collaborator(s)'s intellectual property rights, are protected. Copies of abstracts must be provided to CTEP for forwarding to Collaborator(s) for courtesy review as soon as possible and preferably at least three (3) days prior to submission, but in any case, prior to presentation at the meeting or publication in the proceedings. Press releases and other media presentations must also be forwarded to CTEP prior to release. Copies of any manuscript, abstract and/or press release/ media presentation should be sent to:

Email: [contact]

The Regulatory Affairs Branch will then distribute them to Collaborator(s). No publication, manuscript or other form of public disclosure shall contain any of Collaborator's confidential/ proprietary information.

13. STATISTICAL CONSIDERATIONS

13.1 Study Design/Endpoints – Determination of the Maximum Tolerated Dose

The primary endpoint of this study is to determine the RP2D dose of daily oral IPdR administered alone for 7 days and then concurrently with conventionally fractionated whole brain radiation therapy (WBRT) for 3 weeks in patients with brain metastases. In order to determine the RP2D, an expansion cohort will be utilized, which is outlined in detail in sections 5.1.3. Dose limiting toxicity (DLT) is fully defined in section 5.2.

13.2 Sample Size/Accrual Rate

Any estimate of accrual in a dose escalation study is difficult because the study team does not know when the MTD will be found. In the original design, assuming both Parts 1 and 2 require 3 dose escalations to determine the MTD, the sample size was estimated between 17 (1 patient at 2 levels and 3 at the third level in Part 1 and 3 patients at the first level, 6 at the second level, and 3 at the third in Part 2) and 27 (3 patients at each of the 3 levels in Part 1 and 6 at each level in Part 2). Six patients were planned to be accrued at the MTD in the expansion cohort to permit the analyses of the %IUDR-DNA cellular incorporation in circulating granulocytes and tumor once MTD has been determined. This would also help narrow the confidence interval on the estimate of incidence of toxicity at the MTD which makes the expected accrual between 23 and 33. The low number of the expansion cohort was chosen considering the logistics of arranging for a study screening, consent, registration, biomarker testing and limiting total patient numbers/budget. The maximum accrual will be 47. This includes 7 in Part 1 (1 patient at the first 4 levels followed by 3 at level IE), 30 in Part 2 (6 patients at each of the 5 dose levels), 6 additional patients at the MTD, and an additional 4 to account for replacements.

In the proposed amendment #6 (Dec. 2017), to accelerate accrual, the dose-escalation design was changed such that part -1 was truncated at dose level IB, with one patient accrued at each dose-level (total 2). The study was opened to part-2 as a modified 3+3 design with three dose-levels accruing up to 6 patients each depending on the occurrence of DLT. Thereby, the number of patients accrued in part 1 and 2 will range from 8 (2+6) to 20 (2+6+6+6).

Till date (December 2019), 2 patients have been accrued in part 1 (1+1), 3 patients at dose-level 2A and 1 patient at dose-level 2B. In the current proposed design amendment #7, since dose-level 2B is being stopped with one patient and dose level 2A will be re-opened for additional 3 patients, the expected accrual in the two parts will range from 9 (2+7) to 15 (2+7+6) patients. Ten patients will be accrued at the RP2D in the expansion cohort to help narrow the confidence interval on the estimate of incidence of toxicity at the RP2D which makes the range of accrual between 19 and 25. The maximum accrual will be 25 patients. Up to a total of six patients in the expansion cohort will be analyzed for the %IUDR-DNA cellular incorporation in circulating granulocytes and tumor once RP2D has been determined.

Assuming an accrual rate of 1-2 patients per month, for a minimal accrual of 18 patients

will require approximately 18-24 months. Additionally the study will close for evaluation of DLT leading to a total estimated study time of 30 months

Both men and women of all races and ethnic groups, when appropriate, will be eligible for these studies. Subject selection is equitable if they meet the inclusion and exclusion criteria. In conformance with the National Institutes of Health (NIH) Revitalization Act of 1993 (amended in October, 2001) with regard to inclusion of women and minorities in clinical research, possible interaction between race/ethnicity and treatment have been considered. Based on the historical number of brain metastases patients who receive WBRT per month at the University of Maryland and Mayo Clinic, there are expected to be approximately 15% of participants classified as minorities by race and 50% of participants to be female.

PLANNED ENROLLMENT REPORT

Racial Categories	Ethnic Categories				Total
	Not Hispanic or Latino		Hispanic or Latino		
	Female	Male	Female	Male	
American Indian/ Alaska Native	0	1	0	0	1
Asian	1	1	0	0	2
Native Hawaiian or Other Pacific Islander	0	0	0	0	0
Black or African American	1	2	1	0	4
White	19	19	1	1	40
More Than One Race	0	0	0	0	0
Total	21	23	2	1	47

13.3 Stratification Factors

None.

13.4 Analysis of Secondary Endpoints

13.4.1 Tumor Response

Best Response is defined to be the best objective status recorded from the start of the treatment until disease progression/recurrence. The patient's best response assignment will depend on the achievement of measurement criteria as described in section 11.0. Responses will be summarized by simple descriptive summary statistics delineating complete and partial responses as well as stable and progressive disease in this patient population (overall and by tumor group). The number of responses may indicate further evaluation for specific tumor types in a Phase 2 setting. Only patients in Part 2 of the study will be included in this evaluation.

13.4.2 Pharmacokinetics

The pharmacokinetics of daily oral dosing of IPdR for 28 days will be explored.

13.4.3 Biomarkers

Biomarker data will be explored in a simple descriptive manner as data are limited in this small phase 1 study.

13.4.4 Intracranial progression free survival (icPFS) and Overall Survival (OS)

These will be explored using the Kaplan-Meier method. For estimation of icPFS, patients alive without intracranial progression at last follow-up will be censored at the date of the last radiologic assessment whereas intracranial progression or death will be scored as events. The icPFS estimates at 6 months with their standard error of the estimate will be reported. For calculation of OS, patients alive at last follow-up will be censored.

13.4.5 Incidence of delayed neurological toxicity at 2, 4 and 6-months (\pm 1 week) post-completion of WBRT (for patients without intracranial progression) including:

- a. Delayed-recall through HVLT-R**
- b. Quality of life as measured by the FACT-BR**

REFERENCES

1. Posner, J.B. and N.L. Chernik, Intracranial metastases from systemic cancer. *Adv Neurol*, 1978. 19: p. 579-92.
2. Stewart, B.W., P. Kleihues, and I.A.f.R.o. Cancer, *World cancer report*. Vol. 57. 2003: IARC press Lyon.
3. Gaspar, L.E., et al., Validation of the RTOG recursive partitioning analysis (RPA) classification for brain metastases. *Int J Radiat Oncol Biol Phys*, 2000. 47(4): p. 1001-6.
4. Nussbaum, E.S., et al., Brain metastases. Histology, multiplicity, surgery, and survival. *Cancer*, 1996. 78(8): p. 1781-8.
5. Sperduto, P.W., et al., Summary report on the graded prognostic assessment: an accurate and facile diagnosis-specific tool to estimate survival for patients with brain metastases. *J Clin Oncol*, 2012. 30(4): p. 419-25.
6. Tsao, M.N., et al., Whole brain radiotherapy for the treatment of newly diagnosed multiple brain metastases. *Cochrane Database Syst Rev*, 2012. 4: p. CD003869.
7. Young, D.F., et al., Rapid-course radiation therapy of cerebral metastases: results and complications. *Cancer*, 1974. 34(4): p. 1069-76.
8. Rades, D., et al., Dose escalation beyond 30 grays in 10 fractions for patients with multiple brain metastases. *Cancer*, 2007. 110(6): p. 1345-50.
9. Chao, J.H., R. Phillips, and J.J. Nickson, Roentgen-ray therapy of cerebral metastases. *Cancer*, 1954. 7(4): p. 682-9.
10. Gaspar, L.E., et al., The role of whole brain radiation therapy in the management of newly diagnosed brain metastases: a systematic review and evidence-based clinical practice guideline. *J Neurooncol*, 2010. 96(1): p. 17-32.

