1.2 Secondary Objectives

1.2.1 To observe and record anti-tumor activity to IPdR-mediated radiosensitization. Although the clinical benefit of this drug used before and during radiation therapy has not yet been established, the intent of offering this treatment is to provide a possible therapeutic benefit, and thus the patient will be carefully monitored for tumor response at 6 months using RECIST criteria in addition to safety and tolerability. Only patients in Part 2 of the study will be included in this evaluation.

1.2.2 To estimate 6 month intracranial progression-free survival (PFS) in brain metastasis cancer patients who receive daily oral IPdR x 28 days and WBRT.

1.2.3 To establish the pharmacokinetics of daily oral dosing of IPdR times 8 days.

1.2.4 To evaluate safety and tolerability of oral IPdR x 28 days and WBRT.

1.2.5 To estimate the incidence of delayed neurological toxicity at 2, 4 and 6 months (\pm 1 week) post-completion of WBRT (for patients without intracranial progression) including:

- Delayed-recall through HVLT-R
- Quality of life as measured by the FACT-BR.

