5.5 Duration of Follow Up

Patients will be evaluated for up to two years from the study registration or until death, whichever occurs first. From the date of completion of WBRT, follow-ups would be done through clinic visits every 2 months (\pm 1 week) for the first 6 months, every 3-4 months (\pm 2 weeks) for the next 6 months and every 6 months (\pm 3 weeks) for the next one year. After the first DLT assessment visit (primary endpoint), these visits in the first 6 months can be performed at an outside institution if appropriate research staff (credentialed and registered as a study team member) is available to complete adverse event and neurocognitive evaluation. After the first 6 months of follow up, clinic visits may be replaced by phone calls or visits at an outside institution, if not felt feasible for logistic reasons. Follow up notes or documentation of phone calls must be included in the study chart. Patients removed from study for unacceptable adverse event(s) will be followed until resolution or stabilization of the adverse event.

Follow-up MRI at 6 months (\pm 2 weeks) from the completion of WBRT is required to assess intracranial treatment response and disease control. As guided by institutional practices, MRIs are also recommended to be performed during follow-up visits every 2 months (\pm 1 week) for the first 6 months and every 3-4 months (\pm 2 weeks) for the next 6 months from the completion of WBRT.

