- e. On Days 15 and 22 of the 28-day dosing schedule, blood will be obtained just prior to the po drug administration and then at 30, 60, 120 and 240 minutes following po dosing. A five minute positive or negative margin on each of the above times on Day 1 (30 through 240 minutes) is acceptable.
- f. %IUDR-DNA cellular incorporation. Sample collection will be prior to study (Day 1) and at Days 8, 15, 22 and 29 of the 28-day treatment followed by first two-month follow up.
- g. Follow-up MRI at 6 months (\pm 2 week) from the completion of WBRT is required. As guided by institutional practices, MRIs are also recommended during follow-up visits every 2 months (\pm 1 week) for the first 6 months and every 3-4 months (\pm 2 weeks) for the next 6 months from the completion of WBRT. If progressive disease is seen on MRI, subsequent evaluations are not required for study.
- h. For patients accrued to part 2 of the study, please send anonymized pre- and post-treatment (up to 6 months from the date of completion of WBRT) scans via FTP or hard copy CD to the study PI for central review of response.
- i. From the date of completion of WBRT, follow-up visits to be done every 2 months (\pm 1 week) for the first 6 months, then and are recommended every 3-4 months (\pm 2 weeks) for the next 6 months then every 6 months (\pm 3 weeks) for the next one year. These visits can be performed at an outside institution if appropriate research staff (credentialed and registered as a study team member prior to the evaluations) is available to complete adverse event, neurocognitive testing and QOL evaluation. After the first 6 months of follow up, clinic visits may be replaced by phone calls or visits at an outside institution. Follow up notes or documentation of phone calls must be included in the study chart.
- j. Neurocognitive and quality of life evaluation to be performed at the D35 assessment time-point and then during follow-up visits every 2 months (\pm 1 week) for the first 6 months from the date of completion of WBRT (for patients without intracranial progression). A total of 5 neurocognitive and quality of life evaluations will be performed: Baseline, D35, 2-, 4- and 6- months from the date of completion of WBRT.
- k. To be performed only if feasible if the patient is removed from the study.
- l. Perform biopsy only if patient has an easily accessible tumor.
- R. Research.

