Study personnel administering the HVLT must be previously credentialed in performing neurocognitive testing through existing mechanisms within cooperative groups including but not limited to participation in a prior NRG or Alliance or any other cooperative group study. Email a copy of this certification to the study PI, [name]. The PI may also approve other measures as applicable including but not limited to credentialing through training arranged by the study PI (or representative) or participating site's internal training. Each participating site should review the credentialing process with the study PI (or representative) prior to site activation. This requirement is necessary before any patients can be enrolled into the study at the site; see Site Registration, section 4.2.2. These assessments can be performed at an outside institution if appropriate research staff (credentialed and registered as a study team member prior to the evaluations) is available to complete adverse event and neurocognitive evaluation.

Scoring of HVLT-R

1. HVLT-R Delayed Recall

Patient scores on the HVLT-R delayed recall section have an integer range from 0 to 12 with lower scores indicating declining cognitive function. The score is the number of words a patient can recall from a list of 12 words. The change in score

from baseline to 2-, 4- and 6- months ranges from - 12 to 12. Change scores from 1 to 12 indicate declining cognitive function. A change score of 0 indicates preserved cognitive function. Change scores from -1 to -12 indicate improved cognitive function and are not expected.

2. HVLT-R Free Recall

Patient scores on the HVLT-R free recall section have an integer range from 0 to 36 with lower scores indicating declining cognitive function. The score is the number of words a patient can recall from a list of 12 words in three trials.

3. HVLT-R Delayed Recognition

10.1.2 Patient scores on the HVLT-R delayed recognition section have an integer range from -12 to 12 with lower scores indicating declining cognitive function. The score is the number of correctly identified words from the list of 12 words minus the number of incorrectly identified words from the list of 12 words.

10.2 Functional Assessment of Cancer Therapy with Brain Subscale (FACT-BR) for Quality of Life (QOL)

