11. MEASUREMENT OF EFFECT

Although the clinical benefit of IPdR has not yet been established, the intent of offering this treatment is to provide a possible therapeutic benefit, and thus the patients in part 2 of the study (to exclude patients treated at lower doses in part 1 thereby minimizing heterogeneity in response) will be carefully monitored for tumor response in addition to safety and tolerability. Patients with measurable disease will be assessed by standard criteria noted below. Each eligible patient must have at least one measurable lesion that will be included in the radiation treatment volume. If the measurable disease is restricted to a solitary lesion, the presence of malignancy must be confirmed by cytology/histology. Tumor lesion(s) included within the high dose radiation treatment volume ($\geq 95\%$ isodose line) will be considered as the target lesions for response evaluation. Patients with measurable disease will be assessed by standard criteria. For the purposes of this study, patients should be evaluated at baseline at 6 months (± 2 weeks) from the completion of WBRT. As guided by institutional practices, MRIs are also recommended during follow-up visits every 2 months (± 1 week) for the first 6 months and every 3-4 months (± 2 weeks) for the next 6 months from the completion of WBRT.

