11.1.6 Intracranial Progression-Free Survival

The date at which intracranial progression is radiographically identified will be used to calculate the intracranial PFS. Intracranial PFS will be measured from the date of start of treatment to time of progression or death, whichever occurs first. Intracranial PFS will be assessed 2, 4, 6 and 8 months after the initiation of study therapy. If intracranial progressive disease is seen on MRI, any subsequent MRI scans will be performed as clinically indicated standard of care.

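### Delayed neurotoxicity at 2 and 4 months is restricted to patients without intracranial progression, but no MRI is required at those visits, so the analysis set depends on local scanning practice

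*Combined protocol and SAP*

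**What the plan says.** - **Endpoint.** Section 1.2 sets the objective: "To estimate the incidence of delayed neurological toxicity at 2, 4 and 6 months" after WBRT. Section 13.4.5 repeats the time points and limits the population ("post-completion of WBRT (for patients without intracranial progression) including" delayed recall and FACT-BR). It is a heading with two instruments. It gives no analysis method, no attribution step and no rule for a patient who was not scanned.
- **Tests.** The Section 10 calendar notes fix the testing visits: "A total of 5 neurocognitive and quality of life evaluations will be performed: Baseline, D35, 2-, 4- and 6- months" after WBRT, with a window of 1 week either side for the follow-up visits.
- **Decline.** Each patient is his or her own control. For delayed recall, Section 10.1.1 says "Change scores from 1 to 12 indicate declining cognitive function". Section 10.2 treats 5 points on FACT-BR as meaningful.
- **Imaging.** Section 5.5 makes one follow-up MRI obligatory: the scan at 6 months (2 weeks either side) "from the completion of WBRT is required to assess intracranial treatment response and disease control". For the earlier visits it says "As guided by institutional practices, MRIs are also recommended to be performed during follow-up visits every 2 months". Section 11 says the same ("As guided by institutional practices, MRIs are also recommended during follow-up visits every 2 months"), as does note g of the calendar.
- **Dating of progression.** Section 11.1.6, on intracranial PFS, says "The date at which intracranial progression is radiographically identified will be used to calculate the intracranial PFS". It adds that this endpoint is assessed 2, 4, 6 and 8 months after therapy starts, without saying that a scan is obligatory at those times.

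**The concern.** The restriction appears intended to keep tumour effects out of a treatment-toxicity estimate. It can do that only if progression status is known when the test is given. At months 2 and 4 the protocol guarantees the test but not the scan.

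Two hypothetical patients with the same disease course show the result. Both fall from 9 to 5 words on delayed recall at month 4, and both have new lesions by then. One site scans at month 4, sees the lesions, and the patient leaves the analysis set. The other site does not scan, no progression is on record, and nothing in Section 13.4.5 removes the patient. An optional scan has separated them.

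The study has one arm, so no comparator shows how much decline comes from the metastases. At stake are the interpretability of a secondary safety estimate and its comparability across sites.

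**Working it through.** The plan gives no expected rate, precision or sample size for this endpoint, so there is no figure to reproduce. The check has two parts.

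**1. Schedules side by side**

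| Visit after WBRT | HVLT-R and FACT-BR | MRI |
|---|---|---|
| 2 months | scheduled, ± 1 week | recommended, ± 1 week |
| 4 months | scheduled, ± 1 week | recommended, ± 1 week |
| 6 months | scheduled, ± 1 week | required, ± 2 weeks |

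The gap is at months 2 and 4. At month 6 the scan is required, though the windows let scan and test lie up to 2 + 1 = 3 weeks apart.

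Section 11.1.6 does not close the gap. It mandates no scan and runs from the start of therapy. The schema ends WBRT on day 26, and 26/30.44 = 0.85 months, so the tests fall about 2.85, 4.85 and 6.85 months from the start. Scans at 2, 4 and 6 months from the start would precede each test by almost a month.

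**2. Illustrative size**

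Inputs:
- 12-month intracranial control with WBRT, c = 0.85 (Section 2.1).
- Constant hazard, with the clock starting at day 1: assumptions.
- Decline rate in truly progression-free patients, b = 0.20 to 0.30: assumption.
- Decline rate in progressing patients, h = 0.60 to 0.80: assumption.
- Nobody scanned before month 6: worst case.

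Share progressed by time t in months: p = 1 − c^(t/12).
- Month 2: 1 − 0.85^(2.854/12) = 3.8%.
- Month 4: 1 − 0.85^(4.854/12) = 6.4%.
- Month 6: 1 − 0.85^(6.854/12) = 8.9%.

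Observed incidence = (1 − p)·b + p·h, so the shift is p·(h − b). At month 4:
- Smallest: 0.064 × (0.60 − 0.30) = 0.019. A true 30% reads 31.9%, a relative increase of 0.019/0.30 = 6%.
- Largest: 0.064 × (0.80 − 0.20) = 0.038. A true 20% reads 23.8%, a relative increase of 0.038/0.20 = 19%.

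At month 2 the shift is 0.038 × 0.30 = 0.011 to 0.038 × 0.60 = 0.023.

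Among the 16 patients planned at the RP2D (Section 5.1.3), the month-4 shift is 16 × 0.019 = 0.3 to 16 × 0.038 = 0.6 of a patient. It shrinks roughly in proportion as more patients are scanned. It grows if progression is more frequent: each further 5 percentage points of unseen progression adds 0.05 × 0.30 = 1.5 to 0.05 × 0.60 = 3 points.

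**The case against.** **The plan never says that such a decline is scored as toxicity.** This stands. A reader might infer that declines from unseen progression are counted as IPdR plus WBRT neurotoxicity. Section 13.4.5 contains no scoring or dating rule, and the radiographic dating in Section 11.1.6 is stated for intracranial PFS only. Section 11.1.7 has files and images reviewed together at study completion, so an analyst would hold the month-6 scan and could apply it retrospectively. What the documents support is that the classification is unspecified. That still leaves the choice to be made after the data are seen.

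**Interim imaging is intended.** Two-monthly MRI is recommended, Section 11.1.6 speaks of assessments at 2, 4, 6 and 8 months, and a declining patient may be scanned clinically. This limits the problem to unscanned patients, whose share is unknown. It does not remove it, because none of these passages requires a scan.

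**The effect is small.** On the working above it is less than one patient in 16. This stands as an illustration, but 85% may be optimistic. The title of reference 18 shows that WBRT was added to radiosurgery in patients with 1 to 3 metastases, and Section 2.5.1 expects worse outcomes in this trial's population.

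**The obvious remedy creates the opposite bias.** Letting the next MRI decide each earlier result conditions on the future. With only the required scan, (8.9 − 3.8)/8.9 = 57% of patients progressed by month 6 would still have been progression-free at month 2, under the same model. Their genuine early declines would be dropped, which lowers a safety estimate. This stands and shapes the fix.

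**Conclusion.** The mismatch is confirmed by the text. Followed as written, the month-2 and month-4 analysis sets depend on optional scanning and may include declines due to undetected progression. The direction is upward provided progressing patients decline more often than others.

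The size cannot be derived from the documents. The figure of about 2 to 4 percentage points at month 4 (6% to 19% relative) rests on 85% control, a constant hazard, assumed decline rates and no interim scans.

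A reader might reach a much larger figure by adding the 51% control quoted in Section 2.1 as a lower limit: 1 − 0.51^(4.854/12) = 23.8%, and 0.238 × 0.60/0.20 gives a relative inflation of about 72%. That 51% is control without WBRT, whereas every patient here is planned to receive it, so it is not a justified bound. Nor does any passage say that a Phase 2 trial would carry this estimate forward.

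The point concerns a secondary endpoint. The DLT and RP2D rules in Sections 5.1 and 5.2 do not use this restriction. Neither does the DSMB trigger in Section 5.1.3 (delayed grade 3 or higher neurotoxicity or extra-cranial radiation toxicity above 20%).

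**What to change.** Add one paragraph to Section 13.4.5 that places each 2-, 4- and 6-month HVLT-R or FACT-BR result in one of three classes:

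- **(a) Confirmed progression-free:** an MRI at or after the test shows no intracranial progression.
- **(b) Progression documented** on or before the test.
- **(c) Indeterminate:** there was no MRI at the visit and the next MRI shows progression, or there is no later MRI.

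State which scan counts as the visit scan (the protocol windows would serve), how a visit scan taken just before or just after the test is handled, and which cut-offs count as decline.

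Report the number of results and the number of declines in each class. Give the incidence in (a) alone and in (a) plus (c). A later progressing MRI then does not by itself remove an earlier decline, and the reader sees how far unknown status could move the estimate. The two figures are not strict bounds, because class (a) favours patients who lived long enough to be scanned.

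Separately, reconcile the assessment times in Section 11.1.6 with the imaging schedule in Sections 5.5, 10 and 11.

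The cost is one paragraph and one derived variable, using data already collected and no new scans. The drawbacks are small cells and some results that stay indeterminate. The latter may be common, since Section 2.1 quotes median survival of 2.3 to 7.1 months by prognostic class.
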